2.1. Study Objective

2.1.1. Primary Objective

The primary objective of this study is to validate that changes in the design of the [REDACTED] tampons meet defined user needs. The primary objective will have been met if the following criteria are met:

- Test tampon elongation rate is the same as or better than the reference tampon for each absorbency, where same is defined as test tampon elongation rate \leq reference tampon elongation rate.
- Product tolerability is deemed to be acceptable based on review of the results.
- Diary responses have $\geq 96\%$ response rates consistent with each user need for each absorbency. If the rate is lower than 96%, the response rate consistent with the user need related to the test tampon must be the same as or better than the response rate of the reference tampon, where same is defined as test tampon response rate \geq reference tampon response rate.

- Interview responses demonstrate that 95% of users are able to identify key information on the package and insert, and able to distinguish between absorbency levels on the wrappers.

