4.1. Introduction

Data processing and tabulation of descriptive statistics described in this SAP will primarily use SAS (release 9.4 or higher). If the use of other software is warranted, the final statistical methodology report will detail what software was used for what purposes.

Continuous (quantitative) variable summaries will include the number of subjects (n) with non-missing values, mean, standard deviation (SD), median, minimum, and maximum.

Categorical (qualitative) variable summaries will include the frequency and percentage of subjects who are in the particular category or each possible value. Summaries may include 95% confidence intervals (CIs) if appropriate. In general, the denominator for the percentage calculation will be based upon the total number of subjects in the study population, either overall or within each absorbency arm, unless otherwise specified.

The minimum and maximum will be reported with the same degree of precision (i.e., the same number of decimal places) as the observed data. Measures of location (mean and median) will be reported to 1 degree of precision more than the observed data. Measures of spread (SD, 95% CI) will be reported to 2 degrees of precision more than the observed data.

Percentages will be presented to 1 decimal place, unless otherwise specified. General exceptions to this rule are values of 100% which will be displayed without any decimal places and zero counts which will not display percentages.

No inferential statistical hypothesis testing will be performed to assess whether the validation criteria have been met. All the analyses described in this SAP to assess whether validation criteria have been met are descriptive.

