8.1. Elongation

Descriptive statistics will be reported for the length of elongation of used tampons within each test article type (test or reference tampon), and separately for each absorbency arm, in the MITT population. The number and percentage of used tampons that have elongated will be reported for test tampons and reference tampons. Determination of whether a tampon is considered to have elongated is described in Section 6.1.4. The denominator for the percentage calculation will be based upon the number of used tampons returned within each test article type (test or reference tampon) and within each absorbency arm (regular or super). The 95% CIs for the percentage elongated estimates will be computed using the exact method (Clopper & Pearson, 1934).

In addition, the testing of equality of proportions of elongation between test and reference article types within each absorbency arm will be performed. For this purpose, the difference between proportions will be calculated along with 95% Wald CIs. Pearson chi-square test will be computed in support of hypothesis testing. The samples for comparison will be considered independent.

The following hypothesis will be tested:

H0: $p1-p2=0$. There is no significant difference in the tampon's elongation rate between the test and reference article types within each absorbency arm.

H1: $p1-p2\neq0$. There is a significant difference in the tampon's elongation rate between the test and reference article types within each absorbency arm.

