8.2. Diary Responses

The number and percentage of diary responses will be reported for test tampon diary entries and reference tampon diary entries in the Safety population, and separately for each absorbency arm. Diary responses for individual tampon entries will be summarized separately from diary responses following last tampon use. Diary responses for individual tampon entries were reported specific to each tampon used and were recorded repeatedly for each used tampon throughout a given menstrual cycle. The denominator for the percentage calculation for individual tampon entry diary responses will be based upon the total number of used tampon diary entries within each question and within each test article type and within each absorbency arm. The number of tampons remaining white and when the subject reported having any flow when using the tampon will be summarized within each test article type and within each absorbency arm as well. The denominator for the percentage calculation will be the total number of used tampon diary entries within each question and within each test article type and within each absorbency arm. Diary responses recorded following last tampon use were reported only once per menstrual cycle. The reasons for not inserting the tampon using the applicator will be summarized. The denominator for the percentage calculation for diary responses following last tampon use will be based on the total number of diary entries within each question and within each test article type and within each absorbency arm. Individual diary responses and diary responses recorded following the last tampon will be listed. And additionally, the reasons for not inserting the tampon using the applicator will be presented in a separate listing. The 95% CIs for the percentage of patients who are able to insert each tampon will be computed using the exact method (Clopper & Pearson, 1934).

In addition, the testing of equality of proportions of patients who are able to insert each tampon between test and reference article types within each absorbency arm will be performed. For this purpose, the difference between proportions will be calculated along with 95% Wald CIs. Pearson chi-square test will be computed in support of hypothesis testing. The samples for comparison will be considered independent.

The following hypothesis will be tested:

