Absorbency Arm: Regular	Variable Statistic	Test Tampon (N=XX)	Reference Tampon (N=XX)
Length of Elongation			
n [1]		XX	XX
Mean (SD)		XX.X (XX.XX)	XX.X (XX.XX)
Median		XX.X	XX.X
Min, Max		XX, XX	XX, XX
Elongated [2]			
n [1]		XX	XX
Percentage		XX.XX%	XX.XX%
95% CI for the Percentage [3]		XX.XXX%, XX.XXX%	XX.XXX%, XX.XXX%
Difference in Percentage		XX.XX%	
95% CI for the Difference in Percentage [4]		XX.XXX%, XX.XXX%	
Chi-Square		XX.X	
P-Value		X.XXX	

Abbreviations: CI = confidence interval; MITT = modified intent-to-treat; SD = standard deviation.

Note: Percentages are n/Number of used tampons returned by subjects in the MITT Population within tampon type*100. Length is measured in millimeters (mm). Tampon integrity assessments were performed at the post-use visits which were conducted within 72 hours following the last tampon use for that menstrual cycle. Subjects used each test article type (reference or test tampon) over the course of one menstrual cycle. N is the number of subjects within each article and within absorbency arm.

[1] n is the number of tampons.

[2] Any used tampon with a measurement of elongation >10 mm was considered elongated.

[3] The 95% CIs for the percentage elongated estimates were computed using the exact method.

[4] The 95% CIs for the difference in percentage elongated estimates were computed using Wald method

Reference Listing: 16.2.6.1

Programming Note: Repeat for Absorbency Arm: Super.

[figure not shown]

Table 14.2.2.1
 Summary of Individual Tampon Entry Diary Responses
 Safety Population

Absorbency Arm: Regular	Test Tampon (N=XX)	Reference Tampon (N=XX)
Variable Category		
Able to remove the tampon	XX	XX
Yes	XX (XX.X%)	XX (XX.X%)
No	XX (XX.X%)	XX (XX.X%)
White area remaining on tampon	XX	XX
No areas on the tampon remained white	XX (XX.X%)	XX (XX.X%)
Less than half of the tampon remained white	XX (XX.X%)	XX (XX.X%)
About half of the tampon remained white	XX (XX.X%)	XX (XX.X%)
More than half of the tampon remained white	XX (XX.X%)	XX (XX.X%)
Whole product remained white	XX (XX.X%)	XX (XX.X%)
Flow when using the tampon	XX	XX
No flow	XX (XX.X%)	XX (XX.X%)
Spotting only	XX (XX.X%)	XX (XX.X%)
Light	XX (XX.X%)	XX (XX.X%)
Medium	XX (XX.X%)	XX (XX.X%)
Heavy	XX (XX.X%)	XX (XX.X%)
Tampons remaining white and where subject reported having any flow when using the tampon*	XX (XX.X%)	XX (XX.X%)

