Other	XX (XX.X%)	XX (XX.X%)

Note: Percentages are n/Number of recorded diary entries by subjects in the Safety Population within each question and within tampon type*100. Subject diaries were returned at the post-use visits which were conducted within 72 hours following the last tampon use for that menstrual cycle. Diary responses recorded following last tampon use were reported only once per menstrual cycle. Subjects used each test article type (reference or test tampon) over the course of one menstrual cycle.

n is the total number of diary entries for each section of the table. N is the number of subjects within each article and within absorbency arm.

[1] The 95% CIs for the percentage of patients who are able to insert each tampon using the applicator and for the difference in percentage of patients who are able to insert each tampon using the applicator were computed using the exact method.

Reference Listing: 16.2.6.2.2

Programming Note: Repeat for Absorbency Arm: Super.

[figure not shown]

Table 14.2.3
 Summary of Packaging and Labeling Interview Responses
 ITT Population
 Gynecological Exam Subset

Variable Category	Overall (N=XX)
Able to correctly identify tampon absorbency provided in the regular absorbency box	XX
Yes	XX (XX.X%)
No	XX (XX.X%)
Able to correctly identify the tampon absorbency ranges for the entire line of products on the box	XX
Yes	XX (XX.X%)
No	XX (XX.X%)
Able to correctly identify the Toxic Shock Syndrome warning on the box	XX
Yes	XX (XX.X%)
No	XX (XX.X%)
Able to correctly identify the information that states how long you should use a tampon on the box	XX
Yes	XX (XX.X%)
No	XX (XX.X%)
Able to correctly identify tampon absorbency provided in the super absorbency box	XX
Yes	XX (XX.X%)
No	XX (XX.X%)
Able to correctly identify tampon absorbency provided in the super plus absorbency box	XX
Yes	XX (XX.X%)
No	XX (XX.X%)

Abbreviation: ITT = intent-to-treat.

Note: Only the subset of subjects who were selected to undergo gynecological exams prior to and following tampon use completed the packaging and labeling interview. The packaging and labeling interview was conducted at the Screening/Baseline Visit (Visit 1). Percentages are n/Number of subjects in the ITT Population who belong to the subset of subjects that were selected to undergo gynecological exams and responded to the respective question *100.

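### SAP 8.1 and 8.2 compare the two products as independent samples although each woman uses both, so the nominal 5% and 95% levels cannot be relied on

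*SAP*

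**What the plan says.** The study is a randomised crossover. Within an absorbency arm, each woman uses one product for one menstrual cycle and the other product for the next (SAP 3.1). The sample size section expects 7 usable tampons per woman per product (SAP 3.2; Protocol 11, Sample Size).

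SAP 8.1 takes the returned tampon as the unit of analysis. For each product: "The 95% CIs for the percentage elongated estimates will be computed using the exact method". The products are then compared by the difference in proportions with a 95% Wald interval and a Pearson chi-square test of H0 against H1. Note [4] of Table 14.2.1 agrees: "The 95% CIs for the difference in percentage elongated estimates were computed using Wald method". The section adds: "The samples for comparison will be considered independent".

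SAP 8.2 repeats that sentence and those methods for the question on inserting each tampon with the applicator. That question belongs to the end-of-cycle diary: "Diary responses recorded following last tampon use were reported only once per menstrual cycle". It therefore yields one answer per woman per product. No clustered or paired comparison is planned anywhere else in the SAP.

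SAP 8.2 and its table also disagree on the interval for the insertion difference. The text says "For this purpose, the difference between proportions will be calculated along with 95% Wald CIs", while note [1] of Table 14.2.2.2 says the limits "for the difference in percentage of patients who are able to insert each tampon using the applicator were computed using the exact method".

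The validation decision does not use these tests. SAP 4.1 states: "No inferential statistical hypothesis testing will be performed to assess whether the validation criteria have been met". The criterion in SAP 2.1.1 is that "Test tampon elongation rate is the same as or better than the reference tampon for each absorbency", judged on the observed rates.

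**The concern.** The same women appear in both columns of each comparison, so independence contradicts the design.

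- **Elongation** has two dependencies that act in opposite directions. Tampons from one woman may resemble each other, which makes the true variance larger than the chi-square assumes. A tendency that carries over from one product to the other makes the variance of the difference smaller. The tampon-level exact intervals per product suffer from the first of these.
- **Insertion** has only the second. Its per-product exact intervals are valid, because each woman answers once per product.

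At stake are the two pre-specified hypothesis tests and the intervals and p-values in Tables 14.2.1 and 14.2.2.2. SAP section 1 allows the planned analyses to go into study reports, regulatory submissions and manuscripts, so readers will take them at face value.

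**Working it through.** **Inputs from the documents.** Elongation 0.7% (reference) and 0.2% (test); power 80%; two-sided alpha 0.05; m = 7 tampons per woman per product; 369 women per absorbency. This gives 369 × 7 = 2,583 tampons per type. The SAP prints 2,538, but only the protocol's 2,583 gives the stated total: 2 × 2,583 = 5,166.

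**Reproducing the plan's figure.** The arcsine formula for two independent proportions gives

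h = 2[asin(√0.007) − asin(√0.002)], n = 2(2.8016/h)² = 2,576.5, so 2,577 tampons per type;

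2,576.5/7 = 368.07, rounded up to 369 women. The plan does not name its formula. The pooled normal formula gives 2,812 tampons (402 women), so the arcsine method is inferred from the match. It contains no term for correlation within a woman.

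**Assumption.** The documents give no within-woman correlation (ICC), so 0.02, 0.05, 0.10 and 0.20 are shown. The upper end is demanding. At ICC 0.10 and a 0.7% rate, a second tampon from a woman with one elongation elongates with probability 0.007 + 0.10 × 0.993 = 0.106, about 15 times the average. At 0.20 the ratio is about 29.

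**Elongation: type I error of the chi-square.** Relative to independence, the variance of the difference is multiplied by

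f = 1 + (m − 1)·ICC − m·r·ICC,

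where r is the share of the tendency common to both products. The actual error of a nominal 5% test is 2Φ(−1.96/√f). For example, ICC 0.10 with r = 0 gives f = 1.60 and 12.1%; with r = 1, f = 0.90 and 3.9%. Beta-binomial simulation (369 women, 0.7% in both products, 20,000 replicates) agrees:

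| Tendency across products | ICC 0.02 | 0.05 | 0.10 | 0.20 |
|---|---|---|---|---|
| Product-specific (r = 0) | 6.3% | 8.3% | 12.2% | 18.6% |
| Shared in half the women (r = 0.5) | 5.5% | 6.5% | 7.9% | 11.4% |
| Fully shared (r = 1) | 4.8% | 4.7% | 3.9% | 2.8% |

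A woman-level robust test held 4.5–5.2% in all of these settings.

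**Elongation: interval for the difference.** At 0.7% against 0.2% (8,000 replicates, same four ICCs), coverage was:

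| Tendency | Planned Wald | Robust |
|---|---|---|
| Product-specific | 93.2 / 90.7 / 87.8 / 81.1% | 94.6 / 94.4 / 93.8 / 93.8% |
| Fully shared | 94.0 / 93.0 / 91.7 / 88.8% | 93.8 / 93.7 / 92.6 / 90.5% |

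So the planned interval can under-cover a real difference even where the test is conservative under the null.

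**Elongation: per-product exact intervals.** Coverage at 0.7% is 96.7% at ICC 0, 95.1% at 0.03, 93.7% at 0.05, 90.7% at 0.10 and 85.3% at 0.20. At 0.2% it is 95.6% at 0.05, 93.3% at 0.10 and 88.6% at 0.20. The interval starts conservative, so it falls below 95% only beyond about 0.03–0.05 at the 0.7% rate, and between 0.05 and 0.10 at the 0.2% rate.

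**Power.** With 369 women, a valid woman-level test of 0.7% against 0.2% has power 75 / 70 / 60 / 49% (product-specific), 77 / 73 / 68 / 57% (half shared) or 79 / 79 / 77 / 72% (fully shared) at the four ICCs. The plan states 80%.

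**Insertion.** With one pair per woman and correlation ρ, the variance factor is 1 − ρ, so the actual error is 2Φ(−1.96/√(1 − ρ)): 1.9% at ρ = 0.3 and 0.6% at ρ = 0.5. Simulation (369 pairs, assumed success 96–99%, 40,000 replicates) gives 1.8–2.0% and 0.6–0.7%, with Wald coverage of about 98% and 99%. Over ρ = 0.1–0.5, asymptotic McNemar runs at 4.0–5.2%, mid-p at 1.4–4.6% and exact at 0.4–3.0%. At 99% against 97% and ρ = 0.3, power is 49% for the planned chi-square, 53% for exact McNemar, 63% for mid-p and 64% for asymptotic.

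**The case against.** No decision depends on these tests. SAP 4.1 makes the validation assessment descriptive, the point estimates are unaffected, and SAP 8.1 offers the test only as support. This stands, and it limits the weight of the point.

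The size of the error for elongation is not known. The largest figures need a tendency that is unrelated between products, yet the protocol describes the modified tampon as the same composition with the string moved. A stable trait such as removal technique would carry over, and the test is then close to nominal: 4.8% and 4.7% at ICC 0.02 and 0.05. This also stands, and it makes the upper figures less likely. It does not exclude them. The protocol attributes elongation partly to string placement, which is what differs between the products, and a woman's flow or habits may differ from cycle to cycle. Independence is itself an assumption of zero correlation that the SAP does not justify, whereas a robust variance needs no assumed value.

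For insertion there is no added false-positive risk. That is true; the cost is a greater chance of missing a real difference in a listed user need.

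**Conclusion.** The concern holds and should be fixed, although the validation outcome does not turn on it. The independence statement contradicts the crossover design in both sections.

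For elongation, the direction and size of the error in the comparison are unknown: 2.8% to 18.6% instead of 5% over the assumed ICC range of 0.02 to 0.20, depending on how much of a woman's tendency is shared between products. The per-product exact intervals are safe only at low correlation. For insertion, the comparison is conservative for any positive correlation, and the per-product intervals are sound. The sample size rests on the same assumption, so the stated 80% power is at the favourable end.

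Confidence is high that the flaw exists. Its practical size is uncertain, because the figures rest on 369 women, exactly 7 tampons per product and correlations that the documents do not supply.

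**What to change.** **SAP 8.1.** Delete the independence sentence and write: *Tampons are clustered within women and each woman uses both products. Test minus reference will be reported with a 95% CI and p-value from a woman-level robust variance, with both products of a woman in one cluster. Per-product 95% CIs will be Clopper-Pearson at the effective sample size (tampons divided by the estimated design effect, not below 1).*

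- Name the design-effect estimator (for example, from the variance of woman-level proportions) and set the design effect to 1 when no tampon of that type elongates. In simulation the adjusted interval covered 95.0–98.0% at both rates, ICC 0 to 0.20.
- A bootstrap resampling women is an acceptable alternative.
- A logistic GEE with product and period should be secondary only. About 18 and 5 events are expected (2,583 × 0.007 and 2,583 × 0.002), and the model fails when no test tampon elongates (0.5% to 3.9% of trials at ICC 0 to 0.20).
- The tampon-level chi-square may stay as a labelled sensitivity analysis.
- Change notes [3] and [4] of Table 14.2.1 to match.

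**SAP 8.2.** Delete the independence sentence. Among women who answered for both products, use asymptotic or mid-p McNemar with a Tango paired interval, which excludes 0 exactly when asymptotic McNemar rejects. State that p = 1 when there are no discordant pairs. Keep the per-product exact intervals. Name the paired method in both the text and note [1] of Table 14.2.2.2, which also removes the Wald/exact contradiction.

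**Cost.** SAP wording, three table notes and a few lines of code. The planned listings already carry subject, product code and result. With the estimator above, per-product elongation intervals widen by about 6% at ICC 0.02 and 47–50% at 0.20. Women with only one completed cycle drop out of the paired insertion test. At 99% insertion success the Tango interval is not shorter than the planned Wald interval. With so few events, the robust interval for the elongation difference can still fall somewhat short of 95%, as the coverage figures show.

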8.2. Diary Responses

The number and percentage of diary responses will be reported for test tampon diary entries and reference tampon diary entries in the Safety population, and separately for each absorbency arm. Diary responses for individual tampon entries will be summarized separately from diary responses following last tampon use. Diary responses for individual tampon entries were reported specific to each tampon used and were recorded repeatedly for each used tampon throughout a given menstrual cycle. The denominator for the percentage calculation for individual tampon entry diary responses will be based upon the total number of used tampon diary entries within each question and within each test article type and within each absorbency arm. The number of tampons remaining white and when the subject reported having any flow when using the tampon will be summarized within each test article type and within each absorbency arm as well. The denominator for the percentage calculation will be the total number of used tampon diary entries within each question and within each test article type and within each absorbency arm. Diary responses recorded following last tampon use were reported only once per menstrual cycle. The reasons for not inserting the tampon using the applicator will be summarized. The denominator for the percentage calculation for diary responses following last tampon use will be based on the total number of diary entries within each question and within each test article type and within each absorbency arm. Individual diary responses and diary responses recorded following the last tampon will be listed. And additionally, the reasons for not inserting the tampon using the applicator will be presented in a separate listing. The 95% CIs for the percentage of patients who are able to insert each tampon will be computed using the exact method (Clopper & Pearson, 1934).

In addition, the testing of equality of proportions of patients who are able to insert each tampon between test and reference article types within each absorbency arm will be performed. For this purpose, the difference between proportions will be calculated along with 95% Wald CIs. Pearson chi-square test will be computed in support of hypothesis testing. The samples for comparison will be considered independent.

The following hypothesis will be tested:

H0: $p_1 - p_2 = 0$. There is no significant difference in proportions of patients who are able to insert each tampon between the test and reference article types within each absorbency arm.

H1: $p_1 - p_2 \neq 0$. There is a significant difference in proportions of patients who are able to insert each tampon between the test and reference article types within each absorbency arm.

